5.6.1. Extent of Exposure

The overall treatment exposure (e.g., duration of treatment exposure, number of treatment administrations, and cumulative dose received) and duration of study follow-up time will be descriptively summarized by treatment group defined above based on the safety analysis set.

NCT05197049

5.6.2. Adverse Events

The verbatim terms used in the eCRF by investigators to identify AEs will be coded using MedDRA. Treatment-emergent AEs (TEAEs) are AEs with onset date on or after the date of the first administration of study intervention. All reported AEs which are treatment-emergent will be included in the analysis. For each AE, the percentage of participants who experience at least 1 occurrence of the given event will be summarized by treatment group. Since safety should be assessed relative to exposure and follow-up, all AE summary tables will summarize the average weeks of follow-up and average exposure (number of administrations) for each treatment group.

The following analyses of AEs will be used to assess the safety of participants:

- Frequency and type of AEs by system organ class and preferred term
- Frequency and type of SAEs
- Frequency and type of AEs leading to discontinuation of study intervention
- Frequency and type of AEs associated with the Infections and Infestations SOC, including serious infections. An infection is any AE that was recorded based on the MedDRA system organ class "Infections and Infestations".
- Frequency and type of severe AEs
- Frequency and type of injection-site reactions. A study intervention injection-site reaction is any reaction at a SC study intervention injection site that was recorded as an injection-site reaction by the investigator on the eCRF.
- Frequency and type of related AEs as assessed by the investigator.

*Adverse events may also be summarized as events per 100 subject years of follow-up, which would account for the potential for differences in follow-up times of participants.

Summary tables will provide the count and percentage of participants with 1 or more of the specified TEAEs by treatment group, system-organ class and preferred term.

In addition to the summary tables, listings of participants with treatment-emergent adverse events of special interest, such as, SAEs and TEAEs leading to discontinuation of study intervention will be provided.

AEs of interest, such as, any deaths, possible anaphylactic or serum-sickness like reactions, AEs associated with drug-related hepatic disorders, opportunistic infections, MACE events (cardiovascular death, nonfatal myocardial infarction, nonfatal stroke), tuberculosis, venous thromboembolism, suicidal ideation and behavior, or malignancies, will either be presented in a table, listing, or described in the clinical study report.

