6.5. Dose Modification

6.5.1. Rescue Medication

All participants in the placebo group who meet at least 1 of the following rescue criteria will receive rescue medication:

- CDAI score >220 and <70-point reduction from baseline CDAI at both Week 12 and Week 16
 OR
- SES-CD score increase by at least 50% from baseline at Week 12

Upon meeting at least 1 of the rescue criteria, participants in the placebo group will receive guselkumab CCI at Weeks 16, 20, and 24 followed by guselkumab CCI q8w.

To maintain the blind, participants randomized to guselkumab who meet at least 1 of the rescue criteria will continue their assigned treatment regimen and receive blinded sham rescue matching placebo SC injection at Weeks 16, 20, and 24. Each active study intervention and its matching

placebo are identical in appearance. Details regarding the analysis rules for placebo participants receiving rescue medication will be included in the SAP.

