5.6. Safety Analyses

Safety analyses will be based on the Safety Analysis Set, unless otherwise specified. In general, participants will be analyzed according to their assigned treatment. However, participants assigned to placebo who incorrectly received guselkumab at any time will be analyzed in the guselkumab group from the time they received guselkumab.

For all continuous safety variables, descriptive statistics by intervention group will include the N, mean, standard deviation, median, minimum, and maximum. Categorical variables will be summarized by intervention group using frequency counts and percentages. No formal statistical comparisons are planned.

Safety data, including but not limited to, AEs and changes in laboratory assessments, will be summarized. Treatment-emergent AEs will be summarized by intervention group and Medical Dictionary for Regulatory Activities (MedDRA) system organ class and preferred terms.

Safety data will be summarized through Weeks 12, 24, 48, and the end of the study.

- Safety data limited to the induction period (ie, through Week 12) will be summarized by treatment groups (columns):
 - 1. Placebo
 - 2. Guselkumab^{CCI} \rightarrow ^{CCI} q8w 3. Guselkumab^{CCI} \rightarrow ^{CCI} q4w
 - 4. Guselkumab Combined (columns 2-3)
- Safety data through Weeks 24, 48, and the end of the study will be summarized with the following groups (columns):

1. Placebo (include all placebo participants excluding data after a participant was rescued with guselkumab)

2. Placebo \rightarrow Guselkumab (include placebo participants who were rescued with guselkumab; data in this group occurred after a subject crossed over to guselkumab).

q4w

3. Guselkumab \bigcirc CCl \rightarrow \bigcirc Q8w

→ CCI

- 4. Guselkumab CCI
- 5. Guselkumab Combined (columns 3-4)
- 6. All Guselkumab (columns 2-4)

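### AE tables through Week 48 and end of study commit only to crude percentages over unequal follow-up; the SAP's own rate per 100 subject-years stays optional

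*SAP*

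**What the plan says.** SAP 5.6 summarises safety through Weeks 12, 24, 48 and end of study. After the Week 12 table, the placebo column is "Placebo (include all placebo participants excluding data after a participant was rescued with guselkumab". Post-rescue data go to a column of their own and into the pooled guselkumab column. SAP 5.6 also states: "No formal statistical comparisons are planned".

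SAP 5.6.2 fixes the incidence measure: "Summary tables will provide the count and percentage of participants with 1 or more of the specified TEAEs by treatment group". Protocol 9.4.5 likewise names only the percentage. SAP 5.6.2 adds a committed descriptor, that "all AE summary tables will summarize the average weeks of follow-up and average exposure", and under SAP 5.6.1 the "duration of study follow-up time will be descriptively summarized by treatment group defined above".

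The follow-up-adjusted measure is a starred note: "Adverse events may also be summarized as events per 100 subject years of follow-up". The note goes on to give the purpose of that rate in these words: "which would account for the potential for differences in follow-up times of participants".

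Protocol 6.5.1 starts rescue dosing of placebo participants at Week 16. One criterion is "CDAI score >220 and <70-point reduction from baseline CDAI at both Week 12 and Week 16"; the other is endoscopic worsening at Week 12. Under Protocol 4.1 and SAP 1.2, un-rescued placebo participants are taken off study intervention at unblinding, after the last participant's Week 48 evaluations and the Week 48 lock. Everyone else continues on guselkumab.

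**The concern.** The placebo column keeps every placebo participant in its denominator but observes rescued participants only to about Week 16 and un-rescued ones only to some time after the Week 48 lock. The guselkumab columns are observed to the cut-off. A percentage with at least one event grows with observation time, so at equal risk guselkumab shows the higher figure. The SAP recognises this, names a measure that addresses follow-up length, and leaves it at 'may'.

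Safety is a secondary objective, and readers will compare these columns although they are descriptive. In the equal-hazard model the crude distortion always makes placebo look safer. Leaving the measure open also means the choice can be made after the Week 24 lock, when a limited group of sponsor personnel is unblinded (SAP 1.2).

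**Working it through.** The documents give no AE rate, rescue fraction or safety precision figure, so there is no figure of the plan's own to reproduce on this point.

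**From the documents:** 106 placebo and 212 combined guselkumab participants (Protocol 9.2); rescue from Week 16 (Protocol 6.5.1); treatment to Week 96 (SAP 1.2) or Week 248 (Protocol 4.1), with a follow-up visit about 12 weeks after the last dose.

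**Assumed:** the same constant hazard h per participant-year in both arms, no dropout, fraction r = 20% to 50% of placebo rescued at Week 16. At r = 0 there is no gap through Week 48.

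**Formulas:** P(w) = 1 − exp(−h·w/52). Guselkumab percentage = P(T). Placebo percentage = (1−r)·P(U) + r·P(16), where U is follow-up of un-rescued placebo (U = T through Weeks 24 and 48). Mean placebo follow-up = (1−r)·U + 16r weeks.

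**Crude percentages, no true difference (r = 20% to 50%)**

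| Table | h | Guselkumab | Placebo |
|---|---|---|---|
| Week 24 | 0.1 | 4.5% | 4.2-3.8% |
| Week 24 | 1.0 | 37.0% | 34.9-31.7% |
| Week 48 | 0.1 | 8.8% | 7.7-5.9% |
| Week 48 | 1.0 | 60.3% | 53.5-43.4% |
| End of study, U = 60 weeks | 0.1 | 18.8% (108 weeks) or 39.3% (260 weeks) | 9.3-7.0% |
| End of study, U = 84 to 108 weeks | 0.1 | as above | 15.6-9.0% across the range |

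At h = 0.1 the Week 48 gap is 1.2 to 3.1 participants of 106 (crude ratio 1.15-1.49); at Week 24 it is 0.3 to 0.8. U = 60 is Week 48 plus 12 weeks. Participants enrolled early stay on placebo longer, hence the 84-108 range. Both are assumptions.

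**The SAP's rate at Week 48, h = 0.1.** Placebo subject-years = 106 × 41.6/52 = 84.8 (r = 20%) or 106 × 32/52 = 65.2 (r = 50%). Guselkumab = 212 × 48/52 = 195.7. Expected events are 8.5 or 6.5 against 19.6, so 10.0 per 100 in each column.

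**What a reader can already do.** Percentage divided by mean follow-up in years gives participants with an event per 100 subject-years.
- Week 48, h = 0.1: 8.82/(48/52) = 9.6 against 7.66/(41.6/52) = 9.6 and 5.92/(32/52) = 9.6.
- Week 48, h = 1.0: 65.3 against 66.9-70.5.
- End of study, h = 0.1, U = 60: guselkumab 18.75/(108/52) = 9.0 or 39.35/(260/52) = 7.9, against placebo 9.32/(51.2/52) = 9.5 and 6.96/(38/52) = 9.5. Here the rough adjustment overshoots, because repeat events are not in the counts.

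**When the hazard is not constant.** Guselkumab/placebo ratios at Week 48, r = 20% / 50%, true ratio 1:

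| Departure (both arms) | h | Crude ratio | Rate ratio |
|---|---|---|---|
| Hazard ×2 in Weeks 0-16 | 0.1 | 1.11 / 1.32 | 0.96 / 0.89 |
| Rescue-type participants ×2 | 0.1 | 1.26 / 1.74 | 1.11 / 1.20 |
| Hazard ×3 in Weeks 0-16 | 1.0 | 1.05 / 1.13 | 0.94 / 0.83 |
| Rescue-type participants ×3 | 1.0 | 1.11 / 1.28 | 1.21 / 1.33 |
| Rescue-type participants ×2 | 2.0 | 1.07 / 1.17 | 1.11 / 1.20 |

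In the two h = 0.1 rows the rate is nearer 1. In the last three rows, for common events, it is farther from 1 than the percentage, in either direction.

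**The case against.** The strongest case against is that the SAP already handles most of this. It says safety should be read against exposure, shows average follow-up in every AE table, puts post-rescue data in a separate column, keeps a Week 12 table that rescue does not touch, and plans no safety test. The calculation above confirms that committed content lets a reader remove most of the Week 48 gap. This stands, and it limits the point to a reporting choice. It does not cover the end-of-study table, where the rough adjustment overshoots.

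It is also fair that rescue is response-based, so removal is probably informative, and that the rate can mislead for common events. That stands as a reason to show both measures. It is not a reason to leave the adjusted one optional.

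Two stronger readings are tempting. A reader might infer that the rate is always closer to the truth than the percentage at Week 48; that depends on the event rate and on the departure assumed, neither of which the documents give. A reader might also infer that the imbalance is concealed or that a safety conclusion is invalidated; the committed follow-up figures and the absence of formal comparisons rule that out.

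**Conclusion.** The point holds as a modest one, worth considering. After Week 12 the only committed incidence measure is crude while observation time differs by design. The gain from committing the rate is clearest for the end-of-study table and for less frequent events at Week 48. It is small or ambiguous at Week 24 and for common events. The size depends on a rescue fraction, event rate, constant hazard and zero dropout that are not in the documents; the end-of-study size also depends on how long un-rescued placebo participants are followed and on which treatment horizon applies. No test, estimand or success criterion is affected.

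**What to change.** In SAP 5.6.2, change 'may also' to 'will' for the Week 48 and end-of-study summaries, at least for overall AEs, SAEs, AEs leading to discontinuation, infections and serious infections, and AEs of interest. Use the measure the SAP already names. Show total subject-years for each column, with placebo follow-up ending at rescue, beside the crude count and percentage. Footnote that the rate assumes a constant hazard, counts repeat events (so a few participants can drive it) and does not correct for response-based removal at rescue. Keep the Week 12 table as the clean randomised comparison.

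The cost is an SAP wording change and one extra rate in each reported row and column; limiting it to the categories above avoids adding it throughout the system organ class and preferred term tables. No new data are needed, since follow-up time is already summarised by these columns under SAP 5.6.1.

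Two matters should be reconciled separately before the end-of-study table. Protocol 9.4.5 ends the treatment-emergent window 12 weeks after the last dose, while SAP 5.6.2 sets no end. Treatment runs to Week 248 in Protocol 4.1 but to Week 96 in SAP 1.2. Neither produces the Week 48 gap.

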5.6.3. Additional Safety Assessments

5.6.3.1. Clinical Laboratory Tests

Blood samples for serum chemistry and hematology will be collected. The following tests will be performed by the central laboratory.

Hematology assessments will include but are not limited to the following: hemoglobin, hematocrit, platelet count, total and differential WBC count.

Blood chemistry assessments will include but are not limited to the following: chemistry panel (total and direct bilirubin, ALT, AST, alkaline phosphatase, albumin, total protein, calcium, phosphate, sodium, potassium, chloride, blood urea nitrogen /urea, and creatinine).

The baseline value for a participant is the value closest to but prior to the first dose of study agent. In addition, change from baseline is defined to be the assessment at the post-baseline visit minus the assessment at baseline. There will be no imputation for missing laboratory values.

Clinical laboratory test values are to be graded based on modified National Cancer Institute Common Terminology Criteria for Adverse Events (NCI-CTCAE) version 5.0 (Appendix 3) except ALT, AST, total bilirubin (TBili), and alkaline phosphatase which will be graded using the predefined upper limit of normal (ULN) thresholds. The laboratory tests not included in the table Laboratory Toxicity Grading in Appendix 3 or the predefined ULN thresholds of liver tests will not be presented in the tables or listings.

The following summaries of clinical laboratory tests will be provided for participants in the Safety Analysis Set:

- Laboratory parameters and change from baseline in laboratory parameters (hematology and chemistry).
- Summary of maximum NCI-CTCAE toxicity grade for post-baseline laboratory values for the predefined hematology and chemistry lab parameters except ALT, AST, total bilirubin, and alkaline phosphatase.
- Shift tables for maximum NCI-CTCAE toxicity grade from baseline will be summarized for the predefined hematology and chemistry lab parameters except ALT, AST, total bilirubin, and alkaline phosphatase.
- Summary of maximum postbaseline measurement for ALT, AST, total bilirubin, and alkaline phosphatase relative to ULN threshold.
- Line graphs will also be provided for ALT, AST, total bilirubin, and alkaline phosphatase.

Listings of participants with the following will also be provided:

- Abnormal post-baseline laboratory values of NCI-CTCAE grade \geq 3 except liver tests
- Post-baseline elevated liver tests of ALT or AST \ge 5x ULN, or total bilirubin \ge 2x ULN, or alkaline phosphatase \ge 2x ULN
- Post-baseline elevated liver test with combined ALT or AST ≥ 3x ULN and (total bilirubin ≥ 2x ULN or INR > 1.5) at the same visit.

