5. STATISTICAL ANALYSES

5.1. General Considerations

Statistical testing will be performed at a significance level of 0.05 (2-sided). The Type I error rate will be controlled over the co-primary endpoints, secondary endpoints, and two Week 48 exploratory endpoints (clinical remission at Week 48, endoscopic response at Week 48). For endpoints that are not multiplicity-controlled, nominal p-values will be presented.

- Unless otherwise specified, data from all investigational centers/sites will be pooled for analysis.
- Study Day 1 refers to the day of the first study intervention administration. All efficacy and safety assessments at all visits will be assigned a day relative to this day.

Study day for a visit is defined as:

- Visit date (date of Study Day 1) +1, if visit date is \geq date of Study Day 1
- Visit date date of Study Day 1, if visit date < date of Study Day 1

There is no 'Study Day 0'.

• Baseline is defined as the last observation prior to or on the day of the first study intervention, unless otherwise specified.

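### Laboratory changes and shifts in the Placebo to Guselkumab column are measured from the pre-placebo baseline, so they carry the Week 0 to Week 16 change on placebo into a guselkumab column

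*SAP*

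**What the plan says.** SAP 5.6.3.1 fixes the laboratory baseline: "The baseline value for a participant is the value closest to but prior to the first dose of study agent". The general rule in SAP 5.1 points the same way: "Baseline is defined as the last observation prior to or on the day of the first study intervention, unless otherwise specified". Neither section gives a second baseline for participants who change treatment.

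Two laboratory outputs in SAP 5.6.3.1 use that value directly. For change, "change from baseline is defined to be the assessment at the post-baseline visit minus the assessment at baseline". The shift tables compare maximum grade with baseline, where "toxicity grade from baseline will be summarized for the predefined hematology and chemistry lab parameters except ALT, AST, total bilirubin, and alkaline phosphatase". In SAP Appendix 3, creatinine grades 2 and 3 can also be reached as multiples of baseline.

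SAP 5.6 sets six columns for safety data through Week 24, Week 48 and end of study. Column 2, Placebo to Guselkumab, is defined to "include placebo participants who were rescued with guselkumab; data in this group occurred after a subject crossed over to guselkumab". Column 6, All Guselkumab, pools columns 2 to 4. The same section says that no formal comparisons are planned for safety.

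On timing, Protocol 6.5.1 states: "Upon meeting at least 1 of the rescue criteria, participants in the placebo group will receive guselkumab CCI at Weeks 16, 20, and 24". Protocol Table 2 schedules hematology and chemistry at Week 16 and has assessments done before on-site dosing. It lets the Week 0 sample be omitted if screening laboratory tests were done within the previous 2 weeks.

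**The concern.** Column 2 exists to attribute safety findings to the treatment being taken at the time. Adverse events can meet that aim, because each has an onset date that falls before or after crossover. A laboratory change cannot, because it is a difference between two dates. Here the later date is on guselkumab and the earlier one is before placebo.

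A reader of the column, or of All Guselkumab, would take a change or shift as something that happened on guselkumab. Part of it may have happened during the preceding 16 weeks on placebo. That can produce an apparent laboratory signal, or cancel a real one, in the pooled column that contains every participant exposed to guselkumab.

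**Working it through.** There is no planned figure to reproduce. The check is a reading of the rules, one identity and two ranges.

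**1. Which value is baseline for a rescued placebo participant?** Placebo dosing starts at Week 0, so the last value before the first dose is the Week 0 sample, or a screening sample up to 2 weeks earlier. The SAP does not define study agent. If it meant guselkumab, placebo participants who are never rescued would have no baseline. Where the SAP does mean the first guselkumab dose, as in 5.7.2 (Immunogenicity), it names guselkumab. Pre-placebo is therefore the only workable reading.

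**2. Which values enter column 2?** The first guselkumab dose is at Week 16 and that visit's sample is drawn before it. The first scheduled post-crossover laboratory sample is therefore at Week 20.

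**3. What does the change contain?** Write L(t) for the value at week t. For any post-crossover visit:

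L(t) − L(0) = [L(16) − L(0)] + [L(t) − L(16)]

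The first bracket is the change on placebo. It is present in full at every visit in the column. With the Week 16 pre-dose value as baseline it drops out.

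**4. Share of time since baseline spent on placebo, 16/t, at scheduled laboratory visits:**

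| Visit | Weeks on placebo | Weeks since first guselkumab dose | Placebo share |
|---|---|---|---|
| Week 20 | 16 | 4 | 80% |
| Week 24 | 16 | 8 | 67% |
| Week 32 | 16 | 16 | 50% |
| Week 40 | 16 | 24 | 40% |
| Week 48 | 16 | 32 | 33% |

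**5. Direction.** A value that worsened on placebo and stayed there shows as a worsening in a guselkumab column. Conversely, let L(16) = L(0) + d be an improvement on placebo, followed by a return on guselkumab to L(t) = L(0). The planned change is 0, while the change since guselkumab began is −d. The sign of the bias is not fixed.

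**6. Which outputs are touched.**
- Change from baseline: all parameters, including ALT, AST, bilirubin and alkaline phosphatase.
- Shift tables: the Appendix 3 parameters, but not those four liver tests. A grade that rose on placebo counts only if it is still present at Week 20 or later, because the column holds no earlier data.
- Creatinine: the grade itself can depend on baseline, so its maximum-grade summary and its grade 3 or higher listing can change too.
- Not touched: liver-test maxima and listings against the upper limit of normal, which use absolute thresholds.

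**7. Weight of column 2 in All Guselkumab.** The documents give no rescue rate. For an assumed rescued proportion r of the 106 planned placebo participants, the share is 106r / (212 + 106r):
- r = 20%: 21.2 / 233.2 = 9% (about 21 participants)
- r = 40%: 42.4 / 254.4 = 17% (about 42)
- r = 60%: 63.6 / 275.6 = 23% (about 64)

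**The case against.** The strongest case against is about reach and remedy, since the wording of the baseline rule is clear.

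*Reach.* The placebo-controlled tables through Week 12 have no crossover column. Rescue does not alter columns 3 to 5, and column 2 is shown on its own, so its part in column 6 can be seen. All of it is descriptive. The laboratory risk that Protocol 2.3.1 names is liver injury, and for liver tests only the change-from-baseline summary is affected. All of this stands, and it limits the point. It does not remove it, because the rule followed as written still misattributes change within columns 2 and 6.

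*Remedy.* Neither baseline is neutral. Rescue depends partly on CDAI, in which hematocrit carries a factor of 6 (Protocol Appendix 8). A baseline taken around the rescue decision may therefore be open to regression to the mean and flatter later hematology. Rebaselining also mixes intervals in column 6: at Week 24, 8 weeks on guselkumab for column 2 against 24 weeks for columns 3 and 4. And apart from creatinine, a placebo-period abnormality that persists would still appear in the maximum-grade summary, which does not use baseline. These are fair points. They are reasons to show both baselines rather than replace one with the other.

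*What a reader might infer beyond this.* One might infer that rescued participants probably drifted on placebo. The documents do not show it: the CDAI criterion in Protocol 6.5.1 is lack of improvement, only the SES-CD criterion requires worsening, and no laboratory trends are given. One might also infer that the C-SSRS baseline needs the same change. It does not: SAP 5.6.3.2 sets its own baseline, the maximum over screening and Week 0, and plans a maximum post-baseline outcome and a listing rather than a change or shift table.

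**Conclusion.** The point holds, within limits. In the tables through Week 24, Week 48 and end of study, every laboratory change from baseline in column 2, and in its part of column 6, contains the full Week 0 to Week 16 change on placebo. Shift tables contain it where a placebo-period grade persists to Week 20 or later, and creatinine grading can contain it through its baseline multiples. This is a stated rule that misattributes, not a missing detail.

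The size of the bias cannot be computed. The 9% to 23% weight of column 2 rests on an assumed 20% to 60% rescue rate and planned group sizes. It says how much of the pooled column is exposed to the problem, not how large the error is. A reader might go on to count participants wrongly shown as shifting on guselkumab. That would need a rescue rate, a rate of new abnormalities on placebo and a persistence rate, and the documents give none of them. Nor do they support reading the problem as always exaggerating harm, or as affecting the randomized guselkumab columns.

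It should be corrected, since the correction is cheap, but it does not bear on efficacy, type I error or the Week 12 safety comparison.

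**What to change.** Add to SAP 5.6.3.1: for column 2, and for its members within column 6, laboratory baseline for change-from-baseline summaries, shift tables and baseline-relative creatinine grading is the last value before the first guselkumab dose. The scheduled Week 16 pre-dose hematology and chemistry sample normally supplies it. Show the version based on the Week 0 baseline alongside. Keep the present baseline for all other columns, and leave the C-SSRS baseline as it is.

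Label column 6 by time since first guselkumab dose, or footnote that the intervals differ between its members.

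The cost is one derived baseline flag and one additional version of the affected tables. No new data are needed.
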